1.1 Study design

This study is a 12-month, multicenter, open-label, randomized study with a 12-month additional follow-up and a long-term extension that will consist of:

- A screening period (up to 2 months) starting from informed consent, screening visit, and including successful liver transplantation (LTx).
- Run-in treatment period following the successful transplantation that ends on the day of randomization or randomization failure, at Day 8 (with visit window of ±2 days) post-LTx.
- The primary treatment period (Treatment Period 1) starting at randomization Day 8±2 post-LTx up to Month 12 followed by a 12-month follow-up treatment period (Treatment Period 2) until Month 24 (Figure 1-1).
- The long-term extension period (Treatment Period 3) starting post Month 24 until the end of the study (EOS).

Participants will be consented and screened for eligibility prior to liver transplantation. Consented participants who have met the screening inclusion criteria, undergone a successful liver transplantation and been initiated on a tacrolimus-based regimen that includes mycophenolate mofetil (MMF) and corticosteroids (CS) according to local practice, will enter the run-in period. Transplanted participants who meet the additional inclusion criteria will be randomized at Day 8 ± 2 post-LTx.

At least 128 participants will be randomized at a ratio of 2:3:3 to TAC Control (Arm 1) or one of two maintenance regimens of CFZ533: 600 mg CFZ533 subcutaneous (SC) injections every 2 weeks (Arm 2) or 300 mg CFZ533 SC injections every 2 weeks (Arm 3) combined with MMF and CS (Figure 1-1).

Each CFZ533 arm will have a loading period where CFZ533 will be administered IV in order to rapidly achieve concentrations providing complete CD40-CD40L pathway blockade in target tissues in conditions where CD40 expression levels may be enhanced (Section 4.2 in the Protocol for dose rationale). Participants who do not meet the randomization criteria will be designated screen failures. The screen-failed participants will not be further followed-up in the study.

The study treatments will be as follows:

- Arm 1 (TAC Control): TAC, MMF, and CS will be started in the peri-transplant period and at randomization and will continue up to EOS. Initial tacrolimus target trough levels will be between 5 15 ng/mL based on b.i.d. dosing and will be maintained throughout the run-in period. From randomization onwards, the TAC levels will be adjusted as per local label.
- Arm 2 (CFZ533 600 mg regimen): Loading doses will be 30 mg/kg IV on Day 8 posttransplantation, with a second dose of 15 mg/kg IV on Day 15 and SC administration of 600 mg every 2 weeks will begin on Day 29 with MMF and CS until the EOS.
- Arm 3 (CFZ533 300 mg regimen): A single loading dose of 30 mg/kg IV will be administered on Day 8 and SC administration of 300 mg every 2 weeks will begin on Day 29 with MMF and CS until the EOS.

In CFZ533 Arms 2 and 3, during the immediate peri- and post-transplant period, TAC will be given to provide immunological coverage but must be completely weaned off by Day 22. For details, please refer to Section 6.7.2.2 in the Protocol.

CFZ533 injections will be administered by authorized Investigator/staff at each study visit. After the Month 6 visit (at site), in-home administration may be allowed by a health care provider (HCP). After Month 12 visit, the pre-filled syringes (PFS) use will allow self-administration at home.

The participants in the Control arm will receive their last dose of TAC on the day of the EOS. From EOS onwards, participants will be treated according to local standard of care practice.

For all participants, MMF will be initiated at the time of liver transplantation, mycophenolates should be maintained throughout the study with CFZ533 or TAC; however adaptations are possible in case of signs of over-immunosuppression or intolerance (see Section 6.5.2 in the Protocol).

For all participants after the last study visit (EOS), there will be a 12-week safety follow-up period.

MMF and corticosteroid doses will be administered according to local practice. Corticosteroid use is mandatory until Month 4 has been completed but the initiation and dose are according to

local practice, with a minimum prednisone dose of 5 mg/day or equivalent dose of another oral corticosteroid.

All dose changes must be recorded in the appropriate CRF.

[figure not shown]

[figure not shown]
Figure 1-1 Study design

1.2 Study objectives and endpoints

Table 1-1 Objectives and related endpoints

Objective(s)	Endpoint(s)
 Primary Objective(s) To evaluate the rate of composite efficacy failure (Biopsy Proven Acute Rejection (BPAR), graft loss or death) with CFZ533 600 mg and 300 mg regimens compared to TAC Control at Month 12 post-transplantation. 	 Endpoint(s) for Primary Objective(s) Incidence of composite efficacy failure at Month 12, where BPAR is from biopsy data indicating a rejection activity index (RAI) ≥3 (Appendix 3 in the Protocol).
 Key Secondary Objective To evaluate the renal function (estimated Glomerular Filtration Rate (eGFR) by MDRD-4 formula) with CFZ533 600 mg and 300 mg regimens compared to TAC Control at Month 12 post-transplantation. Secondary Objective(s) To evaluate the composite of BPAR, Death, Graft Loss and Loss to Follow-up with CFZ533 600 mg and 300 mg regimens compared to TAC Control at Month 12 and Month 24 post-transplantation. 	 Endpoint(s) for Secondary Objective(s) Mean change in eGFR from randomization to Month 12. BPAR as above, Death, Graft Loss and Study completion/disposition datasets.

Objective(s)	Endpoint(s)
 To evaluate whether CFZ533 600 mg or 300 mg regimens have lower incidence rates over 12 and 24 months post-transplantation compared to TAC control arm for the following events: BPAR tBPAR AR Treated Acute rejection (tAR) Antibody mediated (humoral) rejection Graft Loss Death To evaluate eGFR and change in eGFR to Month 24 post-transplantation. To assess the safety and tolerability of CFZ533 regimens compared to TAC control at Month 12 and Month 24. 	 Event rates over 12 months and 24 months post-transplantation. To evaluate eGFR values and change from randomization over time. Proportion of participants with: Adverse events Serious adverse events AEs related to study drug Means and mean change over time of: Vital sign parameters Lab parameters Lab parameters (Section 8.4.1 in the Protocol) Proportion of participants with: Premature discontinuation from study Premature discontinuation of study drug Dose interruption
• To assess the pharmacokinetics of multiple doses of CFZ533 over the 12-month and 24-month treatment and explore the dose-exposure relationship.	 Dose adjustment Free CFZ533 plasma concentrations over time (CFZ533-treated participants only).
• To assess the levels of peripheral soluble CD40 at baseline and over the 12-month and 24-month treatment period (to inform target biology, target engagement).	• Total sCD40 in plasma (all participants).
 To evaluate the immunogenicity of CFZ533 by analysis of anti-CFZ533 antibodies (over the 12- month and 24-month treatment period). 	 Semi-quantitative analysis of anti-CFZ533 antibodies in plasma (CFZ533-treated participants only).

2 Statistical methods

2.1 Data analysis general information

Due to the early termination of the study, the analysis plan has been modified and may be different from the Protocol.

The primary analysis will be performed after all participants have completed the Month 12 visit, or prematurely discontinued study before Month 12. These analyses will be performed by a Contract Research Organization, ICON. Interim analyses, detailed in Section 2.13, will be performed also by ICON.

The following general data conventions will apply:

- Cut-off day is defined as the latest study day before or up to which data will be used in the • analysis. Note that safety data collected during the Safety Follow-up period after EOS is reported to Novartis/Safety and will be included in relevant analyses.
- Descriptive statistics will be calculated based on observed values. Missing values will be • presented separately for each parameter or category. Categorical data will be presented as frequencies and percentages. For continuous data, n (sample size), mean, standard deviation, median, 25th and 75th percentiles, minimum, and maximum will be presented.
- BPAR will be based on centrally blinded adjudicated data. All other efficacy • endpoints will also be based on central

lab data.

- AE, SAE, Infection, Serious Infection (including malignancies), CMV information, and • EBV information will be summarized based on all eligible collected events.
- All lab and vital sign tables will include data since baseline (liver Tx) but changes are calculated based on the day of randomization. All summaries are based on central lab data.

Novartis	
SAP	

- Efficacy and liver function analyses are based on all available data including those after study medication discontinuation or as a supportive analysis based only on on-treatment values. Participants are censored for the time-to-event analyses if they do not have an event. For on-treatment analysis, the censoring day is the date of discontinuation of study treatment (defined in Section 2.1.1); for the all-data analysis (regardless of on-treatment or off-treatment), the censoring day is the last contact day.
- Listings will only be provided for variables explicitly indicated in this SAP. Listings will include all available data.

Details about the definition of efficacy and safety events, data handling conventions including "re-aligned" visit windows, imputation of missing dates, and other details about study concepts and terms can be found in Section 5. Note that the visits defined in the protocol are used to guide investigators whereas the "re-aligned" visit windows (Table 5-1) (simply referred to as visit windows hereafter) will be used for the analyses.

2.1.1 General definitions

For the purposes of statistical analysis, "study treatments" are and will be displayed in the outputs as CFZ533 300mg + MMF, CFZ533 600mg + MMF, and TAC + MMF. "Baseline" is defined as the last assessment, including unscheduled assessments, performed prior to liver Tx. All assessments obtained after liver Tx are considered as post-baseline unless otherwise specified. Only centrally adjudicated data will be used for efficacy analyses and laboratory (including vital signs).

In the event that a participant only takes one of the three treatments, the following definitions apply:

- Start of study treatment:
 - a. CFZ533 arms: day of the first loading dose of CFZ533 on Day 8±2 post-LTx.
 - b. Control arm: Day 8 post LTx.
- End of study treatment:
 - a. CFZ533 arms: day of the last dose of CFZ533 +14 days. If a participant in CFZ533 arms discontinues treatment before Day 8±2 (first dose of CFZ533), the rules of control arm apply.
 - b. Control arm: day of the last dose of TAC.

In calculating the duration of treatment, days of permitted interruption of study medication (CFZ, TAC, and MMF) for any reason will be included (see Section 6.5 in the Protocol for details on permitted dose interruption). The entire treatment period is divided into three parts: Treatment Period 1, 2, and 3 (see Section 1.1).

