12.4.1 Definition of primary endpoint

The primary efficacy endpoint is occurrence of composite efficacy failure (BPAR, graft loss, or death) at 12 months post-transplantation based on central pathologist evaluation. If the central pathologist's evaluation is not available, the local pathologist's reading will be used. The estimand is:

- 1. Population: full analysis set
- 2. Endpoint: composite efficacy failure at 12 months
- 3. Intercurrent events: regardless of treatment or study discontinuation, loss to follow-up, or ascites-based dosing adjustment
- 4. Summary measure: the difference in the proportion of participants with composite efficacy failure in a CFZ533 arm compared to control

Note that ascites-based dosing adjustment is not considered a rescue medication because the occurrence of ascites is not due to lack of efficacy. Accordingly, administering CFZ533 to compensate for drug loss caused by ascites cannot be considered rescue medication. In addition, this unscheduled administration will not result in exposure higher than that seen in participants with no ascites.

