2.4.1 Primary endpoint

The primary efficacy endpoint is occurrence of composite efficacy failure (BPAR, graft loss, or death) at 12 months post-transplantation based on central pathologist evaluation (graft loss and death will be from local evaluation). The estimand is:

- Population: defined through appropriate inclusion/exclusion criteria to reflect the targeted population.
- Endpoint: composite efficacy failure at Month 12 post-transplantation, defined as BPAR, graft loss, or death.
- Treatment of interest: the randomized treatment, CFZ533 300 mg + MMF, CFZ533 600 mg + MMF, and TAC+MMF, regardless of treatment or study discontinuation, loss to follow-up, ascites-based dosing adjustment, or administration of CS (treatment policy).
- Summary measure: the difference in the proportion of participants with composite efficacy failure in CFZ533 arms at 12 months post-transplantation as compared to control.

BPAR is defined as an acute rejection confirmed by biopsy within 48 hours of the suspected rejection (preferably within 24 hours) with a rejection activity index (RAI) score \geq 3. Events of rejection which were discovered incidentally during the study (e.g., via optional Month 12 biopsy or standard of care biopsy) with no clinical suspicion of acute rejection will not be included in the assessment of the primary endpoint. Note that ascites-based dosing adjustment is not considered a rescue medication because the occurrence of ascites is not due to lack of efficacy. Accordingly, administering CFZ533 to compensate drug loss caused by ascites cannot be considered rescue medication. In addition, this unscheduled administration aims not to result in exposure higher than that seen in participants with no ascites.

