3.3 Power for key secondary variable

The primary analysis of renal function is based on the FAS. Participants continue to be followed after study drug discontinuation and participants with graft loss or death will have their Month 12 values imputed as described in Section 2.5.3. For treatment comparisons, there will be a

Novartis	For business use only	Page 35
SAP		CCFZ533A2202

randomized sample of 48 and 32 participants in the CFZ533 and control arms respectively after 12 months. Assuming a common standard deviation of 16 mL/min and one-sided $\alpha = 0.10$, there is 63, 73, or 81% power to detect a difference of 6, 7, or 8 mL/min/1.73m² respectively. If the standard deviation is 20, there is 51, 59, or 67% power respectively. The power calcuation is completed by nQuery 8.4 based on two-sample *t*-test with equal variance.

4 Change to protocol specified analyses

Not applicable.

5 Appendix

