5.3.2 Steroid conversion factors

Steroids will be displayed using prednisone equivalent body weight adjusted doses. The doses displayed in the following table are considered equivalent. To determine prednisone equivalent doses, doses will be multiplied by the conversion factor shown in Table 5-8. To adjust the dose, the body weight measured closest to the start of a steroid dose will be used (from vital signs eCRF).

WHO drug code	Preferred Term Corticosteroid	Equivalent Dose [mg]	Conversion Factor
000447xx	Prednisone	5	1
000162xx	Prednisolone	5	1
000496xx	Methylprednisolone	4	1.25
012428xx	Meprednisone	4	1.25
001867xx	Prednylidene	5 5/7	0.875
000319xx	Triamcinolone	4	1.25
000146xx	Cortisone	25	0.2
000286xx	Hydrocortisone	20	0.25
002131xx	Fludrocortisone	2	2.5
000085xx	Betamethasone	0.75	20/3
000664xx	Paramethasone	2	2.5
000160xx	Dexamethasone	0.75	20/3
008827xx	Deflazacort	6	5/6

Table 5-8 Steroids conversion factors

5.4 **Definition/Derivation of Efficacy Variables**

All efficacy endpoints regarding biopsy described will be summarized based on the central pathologists' evaluation of all biopsy readings. If the central pathologist's evaluation is missing, then the local evaluation will be used.

All acute rejections determined by local biopsy reading are recorded in the clinical database on the Liver allograft rejection and Liver allograft biopsy eCRFs. Central pathological reading will be electronically trasnferred.

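### SAP 2.1.1 allows only central data for efficacy, which contradicts the local-reading fallback in SAP 5.4 and Protocol 12.4.1 and the local source for graft loss and death in SAP 2.4.1

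*SAP*

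**What the plan says.** Five places bear on which reading defines BPAR.

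- **SAP 2.1.1:** "Only centrally adjudicated data will be used for efficacy analyses and laboratory (including vital signs". This is the only exclusive wording.
- **SAP 2.1:** "BPAR will be based on centrally blinded adjudicated data". No fallback is mentioned.
- **SAP 2.4.1:** the primary endpoint is "based on central pathologist evaluation (graft loss and death will be from local evaluation". Again no fallback is mentioned, but two of the three components are expressly local.
- **SAP 5.4**, covering the biopsy-based efficacy endpoints: "If the central pathologist's evaluation is missing, then the local evaluation will be used".
- **Protocol 12.4.1**, for the primary endpoint: "If the central pathologist's evaluation is not available, the local pathologist's reading will be used".

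Two further statements affect how these are read. SAP 2.1 sends the reader to Section 5 for "Details about the definition of efficacy and safety events, data handling conventions including" visit windows and related matters. It also warns that, after early termination, "the analysis plan has been modified and may be different from the Protocol". SAP Section 4, "Change to protocol specified analyses", has nothing entered.

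**The concern.** BPAR is one of the three components of the primary endpoint, so it feeds the rule that a CFZ533 arm succeeds if the posterior probability of a difference below 0.15 exceeds 0.80. SAP 2.1.1 and SAP 5.4 classify the same participant differently when a biopsy has been read locally but not centrally: a failure under 5.4, event-free under 2.1.1. SAP 2.4.3 treats a participant without an observed event as censored, so under the literal 2.1.1 rule a missing reading becomes an absence of rejection. That lowers the failure count in whichever arm has the unread biopsies. The trial is open-label and the analysis is run by a contract organisation from this text, so the rule for a missing central reading should not depend on which sentence the programmer follows.

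**Working it through.** **1. The texts side by side.** Take a for-cause biopsy with local RAI of at least 3 and no central reading, in a participant with no graft loss or death.

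| Source | Result for this participant |
|---|---|
| Protocol 12.4.1 | BPAR by local reading: failure |
| SAP 5.4 | BPAR by local reading: failure |
| SAP 2.1 and 2.4.1 | Central is the basis; silent on a missing reading |
| SAP 2.1.1, literally | Local reading not usable: no event |

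Protocol 12.4.1 also bases the endpoint on the central pathologist and then gives the fallback in its next sentence. Being based on central evaluation is therefore compatible with a fallback. Only the word *only* in 2.1.1 is not.

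2.1.1 also fails by its own terms. SAP 5.4.2 takes graft loss from the Graft Loss CRF page and the date of death from the Disposition eCRF. Neither is a central reading, so a literal application would remove two of the three primary components.

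**2. Check of the decision rule.** Inputs from SAP 3.2: 48 v 32 participants, Beta(1/3, 1/3) priors, success if P(θ_CFZ533 − θ_control < 0.15 | data) > 0.80. Enumerating two independent binomials and integrating the posteriors numerically reproduces all 15 cells of SAP Table 3-2 to about 0.001. For example, at 0.11 v 0.103 the stated value is 0.904 and the computed value 0.9040. The point disputes none of these figures; this only validates the rule used next.

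**3. Effect of one event under the SAP 2.4.2 model.** θ = 1 − exp(−λ), with posterior λ ~ Gamma(y + 0.001, t + 0.001), y failures and t person-years. The follow-up formula in 2.4.2 does not stop at the event, so removing an event changes y and leaves t alone. Counts and person-years below are assumptions; the documents give neither.

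| Person-years | CFZ533 v control failures | P(difference < 0.15) | Success? |
|---|---|---|---|
| 40 v 28 | 9 v 3 | 0.741 | no |
| 40 v 28 | 8 v 3 | 0.823 | yes |
| 40 v 28 | 8 v 2 | 0.709 | no |
| 47 v 31 | 10 v 3 | 0.762 | no |
| 47 v 31 | 9 v 3 | 0.836 | yes |
| 47 v 31 | 8 v 3 | 0.896 | yes |
| 47 v 31 | 8 v 2 | 0.816 | yes |

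At 40 v 28, losing one CFZ533 event (9 v 3 to 8 v 3) turns failure into success, and losing one control event (8 v 3 to 8 v 2) does the reverse. At 47 v 31 the CFZ533 flip moves to the step from 10 to 9, and the same control loss no longer changes the call. With the protocol's binomial rule and 3 control events, 9 CFZ533 failures give 0.789 and 8 give 0.866.

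As a simple proportion, one event is 1/48 = 2.1 points in a CFZ533 arm and 1/32 = 3.1 points in control.

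**4. A wider assumed range.** Suppose 5% to 30% of failures had no central reading and were lost. With true rates 0.15 v 0.103 and the binomial rule, the probability of success moves from 0.729 to 0.750–0.862 if lost in both arms, to 0.768–0.920 if lost only in CFZ533, and to 0.710–0.603 if lost only in control.

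**The case against.** The best defence is that the SAP already points to the right rule. Section 2.1 refers the reader to Section 5 for event definitions, 5.4 is the specific derivation section, and it agrees with the Protocol. The 2.1.1 sentence is general, covers vital signs in the same breath, and cannot be applied literally to graft loss or death. A programmer deriving BPAR would probably work from 5.4 and keep the event. This stands as far as likelihood goes: loss of an event is possible, not certain. It does not remove the contradiction, because the SAP states no order of precedence and 2.1.1 excludes a fallback rather than deferring to one.

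SAP 2.4.5 also requires acute rejection summaries and biopsy listings for central and local assessment separately, so a locally proven rejection without a central reading would be visible. That stands too, but visibility in a supplementary table does not settle how the primary endpoint counts it.

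Three stronger readings are tempting and not supported:

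- **That three SAP sections impose a central-only rule.** Only 2.1.1 does. Sections 2.1 and 2.4.1 use the same kind of wording that Protocol 12.4.1 pairs with its fallback.
- **That the empty Section 4 hides a departure from the Protocol.** While 5.4 keeps the fallback, there is no change on this point to list.
- **That rejections were in fact dropped, or that early termination left slides unread.** Protocol 8.3.1 sends for-cause slides to the central reader up to Month 24, and neither document reports a missing reading.

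**Conclusion.** SAP 2.1.1 states a rule that cannot stand with SAP 5.4, Protocol 12.4.1 or SAP 2.4.1, and it should be corrected. Followed literally, it turns a locally proven rejection with no central reading into a non-event in the primary endpoint.

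The size cannot be determined, because the number of biopsies without a central reading is not given. The posterior values are constructed boundary cases with assumed counts and exposure. At 40 v 28 person-years and 3 control events, only the step from 9 to 8 CFZ533 failures crosses 0.80. They show that one biopsy can decide the call near the threshold, not that it did. The study was stopped after the interim analysis and only an abbreviated report remains, which lowers what now depends on the call. The endpoint will still be reported and needs one definition.

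**What to change.** 1. In SAP 2.1.1, replace only the efficacy part of the sentence with: *BPAR is based on the central reading; if the central reading is missing, the local reading is used (Section 5.4); graft loss and death are from local evaluation.* Keep the laboratory rule as its own sentence, since replacing the whole sentence would delete it.
2. In SAP 2.1 and 2.4.1, add a cross-reference to the fallback in 5.4.
3. Report, by arm, how many primary BPARs rest on the local reading.
4. If central-only was intended, delete the fallback sentence from 5.4 instead and list the change from Protocol 12.4.1 in SAP Section 4.

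While editing, check the local BPAR derivation in 5.4.2. As written it asks for a yes both to acute rejection and to acute and chronic rejection, which could itself exclude a purely acute local rejection that the fallback is meant to keep.

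The cost is wording in three places and one count per arm. SAP 5.4 says local readings are already recorded on the Liver Allograft Rejection and Biopsy eCRFs, so no new data are needed.
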